76	8.3	Storage and Drug Accountability of Study Medication(s)	20
77	8.4	Auxiliary Supply	20
78	8.5	Randomization and Blinding.....	21
79	8.6	Breaking of Blinded Codes	21
80	9.	CONCOMITANT ILLNESSES AND MEDICATIONS.....	21
81	9.1	Definitions	21
82	10.	ADVERSE EVENTS	22
83	10.1	Definitions	22
84	10.1.1	Adverse Event (AE).....	22
85	10.2	Severity Assessment Definitions	23
86	10.3	Relationship to study medication Assessment Definitions.....	23
87	10.4	Outcome Categories and Definitions.....	23
88	10.5	Collection, Recording and Reporting of Adverse Events.....	23
89	10.6	Follow-up of Adverse Events	24
90	10.7	Pregnancy	25
91	10.8	Precautions/Over-dosage	25
92	11.	LIABILITY AND SUBJECT INSURANCE.....	25
93	12.	EVALUABILITY OF SUBJECTS	26
94	13.	PREMATURE TERMINATION OF STUDY:.....	26
95	14.	PUBLICATION PLAN.....	27
96	15.	REFERENCES	28
97			
98			
99			
100			
101			

102

103 1. **BACKGROUND AND SIGNIFICANCE:**

104 Insulin degludec (IDeg), an ultra-long-acting basal insulin, is increasingly used to
105 treat patients with type 1 diabetes (T1D). IDeg has a half-life of 25 hours and
106 duration of action exceeding 42 hours in patients with T1D (1,2) and as a result does
107 not require as stringent a dosing schedule as other basal insulins. It has been shown
108 to have a 4-fold lower within-patient variability in its pharmacodynamic response
109 compared to insulin glargine over the 24 hour dose interval (3). The rate of
110 symptomatic and severe hypoglycemia in T1D patients has also been shown to be
111 lower with IDeg than insulin glargine (4). A recently published systematic review
112 and meta-analysis of 15 clinical trials comparing IDeg to insulin glargine showed
113 lower fasting plasma glucose and less nocturnal hypoglycemia with IDeg (5). The
114 total basal insulin dose invariably decreases with the transition to IDeg (6,7). The
115 lower insulin use and lower rate of hypoglycemia may eventually translate into
116 medical cost savings too (8). Moreover, patients have expressed more satisfaction
117 with their regimen and quality of life with IDeg compared to other agents in one
118 study that compared this objectively using questionnaires, before and after transition
119 (9). All of these factors give IDeg an advantage over other basal insulins currently in
120 the market. However, steady state concentration of IDeg is not reached until 2 to 3
121 doses are administered daily, and this may result in greater glycemic variability in
122 the 24 to 72 hours following the initiation of therapy with IDeg (10). There is
123 currently no evidence-based guidance on how to minimize glucose excursions when
124 transitioning patients from their existing basal insulin to IDeg. The package insert for
125 IDeg suggests a 1:1 dose conversion from other basal insulin regimens to IDeg for
126 adult patients. However, this does not account for the time it takes IDeg to achieve
127 steady state and can result in worsening of glycemic control in the 48-72 hours after
128 the transition is made. Many practitioners at the University of Washington Diabetes
129 Clinic have seen better glycemic control within the first 12 to 24 hours in T1D
130 patients in whom we gave 50% of their usual dose of insulin glargine at bedtime
131 along with the first dose of IDeg. This leads to our hypothesis that a bridging therapy
132 involving the use of a reduced amount of patients' prior basal insulin at the time of
133 initiating IDeg will lead to improved glycemic control in the first 24-72 hours on
134 IDeg, minimizing the morbidities associated with hyperglycemia and the need for
135 correctional insulin and also avoiding hypoglycemia resulting from over-correction
136 due to use of additional rapid-acting insulin. Additionally, we will follow what has
137 been done in prior clinical trials of conversion from other basal insulins to IDeg and
138 hence, convert them from their insulin glargine total daily dose to 80% of that dose
139 as IDeg (4). An improvement in the safety and ease of transitioning from the more
140 commonly used glargine to IDeg may greatly encourage more providers and patients
141 to adopt IDeg as the basal insulin of their choice. Another benefit would be knowing
142 how to transition patients back to their outpatient IDeg therapy when they are being
143 discharged home from an inpatient stay and were switched to insulin glargine during
144 their hospitalization, as IDeg is not formulary in many hospitals. The purpose of this
145 pilot study is to gain preliminary evidence of whether bridging with insulin glargine
146 while transitioning to IDeg provides better glycemic results in the transition period
147 compared to direct conversion.

148148

149 2. ENDPOINTS AND OBJECTIVES:

150 Primary endpoint:

151 Change in percent time spent in target glycemic range (TIR, glucose 70-180 mg/dL, both
152 values included) in the 48 hours before and the 48 hours after the 1st dose of IDeg

153 Primary objective:

154 To compare the mean change in percent time in range (as defined by the primary
155 endpoint) between patients who transition directly to IDeg to the mean change in patients
156 who use a bridging dose of insulin glargine along with 1st dose of IDeg.

157

158 Secondary end points:

159 These will include the following data obtained from their CGM download in the 48 hours
160 following the first dose of IDeg as measured as a difference compared to the 48 hours
161 preceding the dose:

- 162 1. Coefficient of variation of percent-time-in-range for each treatment within
163 each group
- 164 2. Nocturnal time in range of 70-180 mg/dL (between mid-night and 0600 hours,
165 both values included)
- 166 3. Percent time above 180 mg/dL (TAR-1), percent time above 250 mg/dL
167 (TAR-2) for each treatment within each group
- 168 4. Percent time below 70 mg/dL (TBR-1), percent time below 54 mg/dL (TBR-
169 2) for each treatment within each group
- 170 5. Number of correction boluses for each treatment within each group

171

172 Secondary objectives:

173 To compare each of the secondary endpoints between patients who use a bridging dose to
174 patients who transition directly to IDeg.

175

176 3. RESEARCH DESIGN AND METHODS

177 3.1 **Study Hypothesis:**

178 Our hypothesis is that among patients who transition from insulin glargine to IDeg, those
179 who use a bridging dose of insulin glargine will not have a significant change, on average,
180 in time spent in target glycemic range during the transition period, whereas, those
181 transitioning directly to IDeg will have a significant change in this parameter. We further
182 hypothesize that those using the bridging dose of insulin glargine will have less
183 hypoglycemia, less hyperglycemia and need fewer correction boluses than the direct-
184 conversion patients during the transition period.

185 3.2 **Study type:**

186186

187 This will be a double-blind, randomized, single-center, proof-of-concept study.
188 Randomization will be stratified by use of insulin glargine once daily or twice daily at
189 baseline. Randomization will be conducted using permuted-block design with a block
190 size of 4, ensuring equal numbers of bridging and non-bridging patients in each of the 2

191 resultant strata after every 4th patient is randomized within a stratum. The 2 strata with
192 blocked randomization within each stratum will result in 4 groups as follows:

193 **1. Bridging Groups:**

194 i. Patients transitioning from once daily insulin glargine to once daily IDeg with
195 a bridging dose of insulin glargine.
196 ii. Patients transitioning from twice daily insulin glargine to once daily IDeg
197 with a bridging dose of insulin glargine.

198 **2. Direct-Conversion Groups:**

199 i. Patients transitioning from once daily insulin glargine to once daily IDeg
200 without a bridging dose of insulin glargine (but with a bridging dose of
201 placebo solution to preserve blinding).
202 ii. Patients transitioning from twice daily insulin glargine to once daily IDeg
203 without a bridging dose of insulin glargine (but with a bridging dose of
204 placebo solution to preserve blinding).

205
206 All patients will be instructed to use their own prescription insulin medications till before
207 the 1st dose of IDeg. On the night they have to transition to IDeg, they will start using
208 study drugs for their basal insulin (see section 3.10.4). Starting with the 1st dose of IDeg,
209 their basal insulin will be from study drug only, till visit #3 (see section 3.10.6), at which
210 time, they will resume their original insulin prescriptions. They will remain on their own
211 prescription short-acting insulin throughout the study. On the night of the transition, all
212 patients will be instructed to take their 1st dose of IDeg and along with this, they will take
213 a second injection from a pre-filled syringe of a pre-specified dose of insulin glargine or
214 matched placebo (normal saline), that participants will collect from Investigational Drug
215 Services Pharmacy (IDS) on the same day. The dose will be calculated ahead of time by
216 study staff on visit 2 (see under section 3.10.2.1). Neither the patients, nor the research
217 staff will be aware of their randomization, which will be done by IDS. Patients will act as
218 their own controls, as we will collect glycemic data from 48 hours prior to the first dose
219 of IDeg, which will be compared to the data seen in the 48 hours after the first dose of
220 IDeg. During this observation period of the 48 hours before and after the first dose of
221 IDeg, no adjustments will be made to the calculated and recommended doses of insulin
222 glargine or IDeg. Patients will be followed for up to 1 week after the first dose of IDeg.
223

224 **3.3 Rationale for study Design**

225 Though IDeg is being increasingly used in clinical practice, there are no guidelines on
226 what is the best way to transition patients from other long-acting insulins, such as
227 glargine, to IDeg. The package insert recommends 1:1 dose conversion from other basal
228 insulins to IDeg, but this does not account for the time taken by IDeg to achieve steady
229 state (typically 48-72 hours). There is no guidance on what to do in those 48-72 hours.
230 Given the time taken for IDeg to achieve steady state, the period of transition from one
231 insulin to another, can result in significant glycemic variation in the 24-72 hours after the
232 first dose. We want to study how best to avoid or minimize this and the option of using a
233 small dose of their original long-acting insulin has anecdotal evidence of success in our
234 practice.

235235

236 **3.4 Study population:**

237 We aim to recruit patients with type 1 diabetes mellitus only. We will screen 50 patients
238 with the plan to randomize approximately 40 patients to start IDeg. The IDS at the
239 University of Washington will randomize patients (1:1) to either receive or not receive a
240 bridging insulin glargine dose along with the 1st dose of IDeg, within the stratified groups
241 of once- or twice-daily insulin-glargine regimens.

242

243 **3.5 Inclusion Criteria**

244 Patients must meet ALL inclusion criteria to be included in the study.

- 245 1. Patient age is 18-75 years.
- 246 2. Diagnosis of T1D of at least 1-year duration.
- 247 3. Has the ability to provide informed consent before any trial-related activities.
- 248 4. Treated with insulin glargine as their basal insulin in the 3 months preceding
249 screening visit.
- 250 5. Stable insulin regimen (defined as change of <20% in the total daily dose of
251 insulin and no change to the basal insulin agent) over the 3 months preceding the
252 screening visit.
- 253 6. Patient willing to dose their basal insulin at bedtime.
- 254 7. Hemoglobin A1c < 9% in the 3 months preceding screening visit.
- 255 8. Able to self-administer their insulin doses.
- 256 9. Able to do self-monitoring of blood glucose using a glucose meter and willing to
257 do this at least 2 times daily for patients using a CGM that requires calibration
258 prior to the study and 4 times daily for patients who were not using a CGM prior
259 to the study.
- 260 10. Agreeable to the use of a continuous glucose monitor (CGM) for the duration
261 required in the study. If already using a CGM prior to the study, then agreeable to
262 wearing the blinded study CGM concurrently during the study period.
- 263 11. Will be reachable by phone and/or email to comply with study procedures.
- 264 12. Will be able to comply with study procedures, per investigator's opinion.
- 265 13. Patient agrees to not use correctional insulin unless BG ≥250 for the 48 hours
266 before and after 1st dose of IDeg.

267

268 **3.6 Exclusion Criteria**

269 Patient must not have ANY of the exclusion criteria to be included in the study.

- 270 1. Patients with eGFR <30 on at least 2 measurements within 1-year of the screening
271 visit.
- 272 2. History of myocardial infarction within 6 months preceding the screening visit.
- 273 3. Patients taking non-insulin medications for the glycemic management of T1D
274 (including metformin, DPP-4 inhibitors, GLP-1 receptor agonists, SGLT-2
275 inhibitors, thiazolidinediones, alpha-glucosidase inhibitors, pramlintide)
- 276 4. Known or suspected allergy to IDeg or one of its excipients.
- 277 5. Pregnant, planning to become pregnant in the next 3 months or breastfeeding.
- 278 6. Participation in a clinical trial with investigational drug within 1 month of the
279 screening visit or at present.

7. Skin condition that prevents the insertion of the CGM.
8. Previously randomized and received drug in this study.
9. Presence of decompensated or poorly controlled psychiatric conditions.
10. Current known or suspected illicit substance use.
11. Any anticipated surgery or procedure in the next 14 days.
12. Patients using U-300 glargine as their basal insulin.
13. Patients using insulin afreZZa as their short-acting insulin.
14. Use of glucocorticoid burst/pulse therapy within 14 days prior to screening visit (chronic stable glucocorticoid doses are acceptable).

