333 As a result, we will recruit participants who are reasonably well controlled on their
334 baseline insulin regimens. We will exclude participants on non-insulin glucose-lowering
335 agents, as these can affect glycemic variability themselves and confound the results. We
336 are not excluding patients with known severe hypoglycemia or hypoglycemia
337 unawareness in this study, as these are the patients who stand to benefit the most from the
338 transition from insulin glargine to IDeg. We are excluding patients with stage 4 or 5 CKD.
339 We will be excluding patients with a myocardial infarction in the last 6 months. These
340 patients will be excluded as they carry a higher risk that hypoglycemia or hyperglycemia
341 may result in mortality.

342

343 **3.10 Visit Procedures**

344 Subjects will be screened for study eligibility and interest in participating in this study
345 (Screening Visit/Visit 1). All subjects will have the study explained to them and sign the
346 informed consent prior to beginning any study procedures. Subjects must meet the
347 inclusion criteria and have no exclusions.

348

[figure not shown]
349 Randomization and treatment will be initiated only once eligibility is confirmed.

350

351 There will be 4 phases to the study:

- 352 • A **screening phase** to establish eligibility that spans from screening visit till
353 insertion of study CGM (up to 2 weeks).
- 354 • A **baseline observation** phase to collect CGM data on their original insulin
355 glargine regimen, starting from insertion of study CGM to first dose of IDeg
356 administration (~3 days)
- 357 • A **treatment phase** starting from 1st to last dose of IDeg and consisting of at least
358 3 days of IDeg therapy (3-7 days).
- 359 • A **follow-up phase** from removal of study CGM to exiting from the study (till up
360 to 7 days after the last dose of IDeg)

3613	2
6	373373
1	374374
3623	375375
6	376376
2	377377
3633	378378
6	379379
3	380380
3643	381381
6	382382
4	383383
3653	384384
6	385385
5	386386
3663	387387
6	388388
6	389389
3673	390390
6	391391
7	392392
3683	393393
6	394394
8	
3693	
6	
9	
3703	
7	
0	
3713	
7	
1	
3723	
7	

ed on d * Could be extended by 2 days if inadequate CGM data noted on day 3 (see section 3.11.4)

3.10.1 Screening Visit (Visit 1):

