Participants will be seen at the research wing of the Diabetes Care Center (DCC) at the University of Washington, Seattle, WA. Research staff will obtain informed consent after explaining study procedures. A detailed diabetes and medical history will be collected from the subjects. Their current medication regimen will be verified from them, particularly the actual number of units of the different insulins they are using. Subjects will undergo assessment of vital signs (pulse, blood pressure, weight, height, BMI) and a focused physical exam. If there is no available record of eGFR within the last year and/or hemoglobin A1c within the last 90 days, these will be obtained by phlebotomy at this visit. 2 tubes of blood (1x 3cc lavender and 1x 4 cc lime green) will be drawn and sent off to measure hemoglobin A1c (by HPLC method) and basic metabolic panel to the UWMC clinical laboratory, if required. Subjects will be instructed to not alter their diet, alcohol consumption or exercise regimen from the time of study CGM insertion till 48 hours after the first dose of IDEG.

If they are considered to be eligible for the study, then the research staff will contact IDS. IDS will then randomize the participant to one of the two arms within the two stratified groups. (Refer to sections 3.5 and 8.5 for details). Research staff will then contact the participant by phone or email to have them return for visit 2 for insertion of the study CGM.

Important considerations for keeping things as uniform as possible in the study are as below:

- We will ensure that all subjects on once daily insulin glargine are taking it at bedtime. Subjects who were taking it in the morning only at screening visit, will be switched to bedtime dosing at least 7 days prior to study CGM insertion.
- We will ensure that subjects on twice daily insulin glargine at screening visit are taking their 2nd dose of the day at bedtime.

395395

396 **3.10.2 CGM insertion visit (Visit 2):**

397 Participant will return to the DCC, within 2 weeks of visit 1, to meet with a research
398 coordinator who will assist with the insertion of the CGM (Dexcom G6). At this visit,
399 study staff will also perform any teaching and training that may be required for the
400 participant to know how to use the CGM device. This visit needs to be conducted before
401 1200 hours. They will be given CGM supplies to last up to 1 week. They will be

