539 **Twice-daily glargine users:** Approximately 24 hours after their last dose of IDeg, they
540 will administer 50% of their original bedtime insulin glargine dose. Approximately 36
541 hours after their last dose of IDeg they will again administer 50% of their original
542 morning insulin glargine dose. Approximately 48 hours after their last dose of IDeg, they
543 will resume their original insulin glargine dosing regimen (i.e. 50% of total dose twice
544 daily).

545

546 Subjects will receive a gift card for \$50 for participation in the study.

547

548 3.10.7 Exit Visit/Telephone encounter #4 (Visit 4):

549 This visit will be approximately 7 days after the study CGM removal (+/- 2 days).
550 Subjects will be called to see if they have any concerns or questions. They will be
551 instructed to follow up with their original endocrinologist for any further insulin
552 adjustments.

553

554 3.11 Assessments for Efficacy

555 On the screening visit (visit 1), if there is no available record of eGFR within the last year
556 and/or hemoglobin A1c within the last 3 months, these will be obtained by venipuncture
557 at this visit. The research team nurse or physician will perform this. 2 tubes of blood (1x
558 3cc lavender and 1x 4 cc lime green) will be drawn and sent off to measure hemoglobin
559 A1c (by HPLC method) and basic metabolic panel to the UWMC clinical laboratory. No
560 extra blood will be collected from the subjects. There will be no other instances of blood
561 collection during the study. These will help ensure that appropriate subjects are enrolled
562 in the study.

563 At the various telephone encounters, study staff will verify that the subjects are following
564 study instructions correctly. Specifically, on Telephone Encounter #2, only if adequate
565 usable CGM data is available on the data uploaded by the patient will they be allowed to
566 proceed with the transition (see section 3.11.4).

567 By measuring the time a patient spends in range (TIR = 70-180 mg/dL), we are assessing
568 the efficacy of the use of IDeg as a basal insulin.

569

570

571 3.12 Assessments for Safety

572 The primary safety concern in this study is the risk of hypoglycemia. Hypoglycemia
573 management will be revised at screening visit to ensure appropriate education and all
574 medications and supplies needed to manage hypoglycemia will be prescribed at screening.
575 Subjects will be instructed that if they see BG <70 mg/dL on their personal CGM that

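### The kidney exclusion needs two eGFR values below 30, but screening plans at most one draw and only when none is on file, so a patient with stage 4 or 5 CKD and fewer than two qualifying values stays eligible under the numbered criteria

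*Combined protocol and SAP*

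**What the plan says.** All references are to the combined protocol and SAP.

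- **Section 3.6, exclusion 1:** the criterion covers "Patients with eGFR <30 on at least 2 measurements within 1-year of the screening" visit. It is the only numbered criterion on kidney function.
- **Section 3.9:** the rationale states the exclusion without a count of measurements: "We are excluding patients with stage 4 or 5 CKD". After a sentence on recent myocardial infarction it adds that these "patients will be excluded as they carry a higher risk that hypoglycemia or hyperglycemia" may result in death.
- **Section 3.10.1:** laboratory work at visit 1 is conditional: "If there is no available record of eGFR within the last year and/or hemoglobin A1c within the last 90 days", the missing results are obtained at that visit. For this, "2 tubes of blood (1x 3cc lavender and 1x 4 cc lime green) will be drawn", for HbA1c and a basic metabolic panel.
- **Section 3.11:** the same rule is repeated, with the statement that no "extra blood will be collected from the subjects. There will be no other instances of blood" collection during the study. The purpose of the tests is given as "These will help ensure that appropriate subjects are enrolled" in the study.
- **Section 7.1, footnote c:** randomisation takes place at the end of the screening visit, once eligibility is established.

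**The concern.** The criterion asks for a pair of low values, while the screening procedure is satisfied with one value of any kind. Where no eGFR is on file, the protocol orders a test whose result cannot meet the criterion, however low it is. Where one low value is on file, nothing requires the second that the criterion needs. Section 3.9 meanwhile tells the reader that stage 4 and 5 CKD are kept out, on what reads as a mortality-risk argument.

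What is at stake is eligibility and safety, not inference. Section 3.12 names hypoglycaemia as the main safety concern, section 3.9 deliberately admits patients with severe hypoglycaemia or unawareness, and section 3.2 allows no change to the calculated basal doses in the 48 hours before and after the first IDeg dose. A group that the rationale means to keep out could enter under those conditions.

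**Working it through.** No figure in the plan bears on this point. The sample size and power statement in section 4 does not depend on it. The check is a count of the eGFR values available when eligibility is decided.

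**Inputs**

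- Qualifying values required: at least 2, each below 30, within one year of screening (3.6).
- Values drawn at screening: 1 if none is on file for the past year, otherwise none required (3.10.1, 3.11).
- Later draws: none (3.11).

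**Formula**

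Let n be the number of eGFR values on file in the past year and d the number that screening must draw, so d = 1 if n = 0 and d = 0 if n ≥ 1. The largest possible number of qualifying values is n + d, reached when every value is below 30. The exclusion can be met only if n + d ≥ 2.

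| On file (n) | Drawn (d) | Most qualifying values possible | Can exclusion 1 be met? |
|---|---|---|---|
| 0 | 1 | 1 | No |
| 1 | 0 | 1 | No |
| 2 | 0 | 2 | Yes, if both are below 30 |
| 3 | 0 | 3 | Yes, if at least two are below 30 |

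**Reading the table**

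1. The planned draw occurs only in the first row, where the total is 0 + 1 = 1. An eGFR drawn because none was on file can never meet the criterion.
2. In the second row one recorded value, even one below 30, removes the need for a test, and the total is 1 + 0 = 1.
3. Only patients who arrive with two or more low values on file are excluded as a matter of rule.

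**One ambiguity.** The and/or wording in 3.10.1 could be read to mean that a patient with one eGFR on file but no recent HbA1c has both tubes drawn. That might yield a second eGFR by accident. It depends on a missing HbA1c, not on the kidney result, so it is not a confirmation step and does not help a patient whose HbA1c is current.

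**Other provisions.** Inclusion 12 concerns ability to comply with procedures. The relevant withdrawal grounds in 3.7 are discretionary and concern patients already in the study. With randomisation at the end of the screening visit, no confirmatory value is planned before allocation.

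**The case against.** The strongest defence is that the two-value requirement is deliberate. A single low eGFR may be transient, and a second value confirms that the impairment is chronic. On this view exclusion 1 is the protocol's working definition of the CKD group named in 3.9, the two sections agree, and a patient with one low value is unconfirmed rather than wrongly admitted. This stands in part. The documents do not define CKD stages, and one value below 30 does not establish stage 4 or 5. A reader might infer that every patient with a single value below 30 is someone 3.9 says is excluded; the text does not support that.

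The defence does not close the gap. If two values are needed, screening must obtain or require the second, and it does neither.

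A second defence is practical. Section 3.10.1 takes a medical history, section 6 has clinicians at the centre identify candidates, and section 3.10 holds randomisation until eligibility is confirmed. Known advanced CKD would probably come to light. This lowers the practical risk in a single-centre pilot with 3 to 7 days of IDeg. But no numbered criterion excludes on a CKD diagnosis, so these steps give staff information without a rule to apply.

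A third point concerns the mortality argument: the sentence in 3.9 directly follows the one on myocardial infarction. Applying it to CKD as well is the natural reading, but it is not explicit.

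**Conclusion.** The point holds as a mismatch between the exclusion criterion, the screening procedure and the stated rationale. An eGFR drawn because none was on file cannot trigger exclusion 1. A patient who truly has stage 4 or 5 CKD and has fewer than two qualifying values on file is eligible under the numbered criteria, contrary to 3.9.

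The affected group is narrow: eGFR below 30 and fewer than two qualifying values in the past year. A reader might infer that everyone with fewer than two values is affected, but patients with eGFR of 30 or more are not excluded under any reading. The documents give neither the prevalence of low eGFR nor the frequency of testing, so no count can be computed. Among the 50 patients to be screened (3.4) the number is probably small.

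The conclusion assumes that the stage 4 or 5 CKD in 3.9 refers to the same population as the below-30 threshold in 3.6, and that staff follow the numbered criteria literally. It has no bearing on the primary endpoint, the randomisation method or power. It is a minor point, worth correcting because it concerns safety and is cheap to settle.

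**What to change.** Reconcile 3.6 (exclusion 1), 3.9, 3.10.1 and 3.11 so that the eGFR evidence screening relies on is capable of triggering the exclusion that 3.9 describes. State what happens before randomisation when the only available eGFR, whether on file or newly drawn, is below 30. If a second measurement remains necessary, the screening procedure and the no-further-blood statement in 3.11 must provide for it; if it does not, 3.6 must say so. How many values define the renal exclusion is for the sponsor and investigator to decide.

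The cost is a short edit to eligibility and screening text, and possibly a few more screen failures. If one value were made sufficient, some of these would be patients whose low value is transient. If a second were required, the cost would be an additional draw for the few patients concerned, and randomisation for them might have to wait for the result.
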